**Self-persuasion – the process of generating one’s own arguments for changing behavior – is an effective approach to influence motivation and behavior.** Based in theories of persuasion and cognitive dissonance, basic research has demonstrated that self-generated arguments are more effective than arguments from an external source. Approaches eliciting self-persuasion have improved diverse behaviors including smoking cessation, dietary behaviors, and safer sex practices. In our own work, self-written arguments had a medium-sized effect on behavioral intentions for regular exercise ( $d = .60$ ); others also found a medium effect for written and verbalized arguments on eating disorder behaviors (hazard ratio = 2.50). Effects of self-persuasion have been shown to persist for 2-3 months to 2-3 years. Some argue that self-persuasion is the most effective way to change behavior because motivation for change comes from within the individual. **Yet, evidence is unclear about the processes underlying self-persuasion that explain why it is effective.** This is particularly true among underserved populations seen in safety-net systems, given that self-persuasion studies to date have been conducted among diverse, but largely well-educated populations.

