**Aim 2. Develop 4 self-persuasion intervention conditions (based on Aim 1 results) that vary by cognitive processing level (parents verbalize vs. listen to arguments) and choice of argument topics (parents choose vs. are assigned topics) and (b) identify which intervention condition is optimal through a controlled proof of concept study that quantitatively examines basic self-persuasion mechanisms (cognitive processing, choice) and qualitatively explores experiences with intervention tasks.**

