### **Analysis Plan for Aim 2:**

**Quantitative Analysis.** Data will initially be examined using univariate statistics and graphical techniques. Continuous measures will be described using medians, means, and standard deviations; dichotomous variables will be summarized as proportions. Across self-persuasion conditions, demographic characteristics will be compared at baseline via two-way ANOVA or chi-square tests, as appropriate. If groups differ on any of these variables, further analyses will be conducted both with and without these variables as covariates to determine whether these demographic variables are of relevance to group differences.

We will compare the effects of choice and cognitive processing on vaccination intentions (primary outcome) using linear regression. Independent variables will be dummy-coded variables based on two main effects (choice: high = 0, low = 1; processing: deep = 0; shallow = 1), plus their interaction. If equivalence assumptions of initial scores and parallel regression slopes for the groups are met, baseline intentions will be included as a covariate to properly model change. If not, repeated measures ANOVA will be used. We anticipate changes in intentions will be

highest in the deep processing, high choice condition, indicating an additive effect. We will also explore the interaction of the two effects. We will use a similar analytic strategy to examine the effects of choice and processing on decisional balance (secondary outcome).

**Vaccination rates.** Using eligibility data, we will assess whether vaccination rates are similar across all clinic sites.

**Qualitative Data Analysis.** We will use the same analytic process described in Aim 1b.

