**Synthesis of Quantitative and Qualitative Analyses.** To determine which self-persuasion condition (1, 2, or 3) is optimal for our safety-net population and will be tested in Stage 3, we will triangulate quantitative and qualitative findings by creating a summary profile for each condition. The optimal condition will be one that has a positive effect on intentions, but also minimizes participants' negative reactions to using the tablet application. A condition that does not affect intentions will not be considered optimal, regardless of its effect on other quantitative and qualitative outcomes. Likewise, a condition that affects intentions but for many participants raises new concerns, is rated as difficult to complete, or takes significant time to complete will not be considered optimal. Drs. [name] and [name] will jointly make this decision in consultation with the team.

**At the end of Stage 2, we will have quantitative and qualitative data that clarify whether it is best to ask parents to verbalize their own arguments, to choose argument topics they prefer, or both, and which self-persuasion condition is optimal in our underserved, safety-net population.** Evidence clarifying which of the two specific mechanisms (deep processing, choice) has an effect, or whether they have an additive effect, will be critical to how we select the optimal self-persuasion condition to implement in Stage 3. For example, if there is an effect of processing but not choice, we would use Condition 2 that has parents verbalize arguments based on assigned topics that are most persuasive rather than allowing them to generate arguments based on chosen topics that may be less persuasive. If there is an effect of choice but not processing, we would use Condition 3 that has parents choose argument topics they want to hear rather than having them go through the more taxing process of generating their own. If both have an effect, Condition 1 will be selected for Stage 3.

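### Aim 2 primary model: with 0/1 codes plus the product term, the coefficients called main effects are simple effects, with a standard error 1.41 times that of the marginal effects when cells are equal

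*Combined protocol and SAP*

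**What the plan says.** Biostatistics, Analysis Plan for Aim 2 (Quantitative Analysis) specifies a linear regression of vaccination intentions, the primary outcome. The independent variables are "dummy-coded variables based on two main effects (choice: high = 0, low = 1; processing: deep = 0; shallow = 1), plus their interaction". Baseline intentions are added as a covariate if the stated assumptions hold; "If not, repeated measures ANOVA will be used". Change in intentions is expected to be "highest in the deep processing, high choice condition, indicating an additive effect". The section then adds: "We will also explore the interaction of the two effects". A similar strategy is planned for decisional balance, the secondary outcome.

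The Aim 2 statement frames the study as an examination of two mechanisms, cognitive processing and choice, without limiting either to one level of the other.

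The synthesis part of the same section uses the results "To determine which self-persuasion condition (1, 2, or 3) is optimal for our safety-net population". It gives examples of the mapping, such as "if there is an effect of processing but not choice, we would use Condition 2". It does not say which contrast defines an effect there.

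**The concern.** The plan attaches the term main effects to coefficients that are not main effects once the product term is in the model. In a 2x2 factorial the reason to cross the factors is that every parent contributes to the estimate of both. A coefficient that compares only two of the four cells gives that up.

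At stake is the mechanism test. An analyst who follows the coding and labels as written would test choice among verbalizers only and processing among choosers only. Real additive effects would then be missed more often than this sample requires.

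The repeated measures ANOVA fallback would conventionally test marginal effects, so the primary and fallback analyses could also answer different questions under one name.

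**Working it through.** The plan gives no standard error, alpha, effect size or power for Aim 2, so there is no figure of its own to reproduce.

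**Inputs from the plan**
- Coding: choice high = 0, low = 1; processing deep = 0, shallow = 1; product term included.
- Cells: Condition 1 deep/high (0,0); Condition 2 deep/low; Condition 3 shallow/high; Condition 4 shallow/low. The numbers follow from the synthesis paragraph and the order in which Stage 2 lists the conditions.
- Sample: 160 in the Project Timeline (40 per cell if equal); 168 in the Stage 2 procedures (42 per cell if equal).

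**Assumptions, not in the plan**
- Equal cells, two-sided 5% tests, additive effects of d SD.
- Baseline-outcome correlation r of 0, 0.5 or 0.7.
- d from 0.4 to 0.6. The Background cites d = .60, where "self-written arguments had a medium-sized effect on behavioral intentions for regular exercise", but that is a different behaviour and is not a design value.

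**Step 1: what the coefficients estimate.** Write E[Y] = b0 + b1·choice + b2·processing + b3·choice·processing. Inverting the 4x4 cell design matrix gives these weights on the means of Conditions 1 to 4:

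| Coefficient | 0/1 coding | -0.5/+0.5 coding |
|---|---|---|
| Choice | -1, 1, 0, 0 | -0.5, 0.5, -0.5, 0.5 |
| Processing | -1, 0, 1, 0 | -0.5, -0.5, 0.5, 0.5 |
| Interaction | 1, -1, -1, 1 | 1, -1, -1, 1 |

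So under the planned coding b1 is Condition 2 minus Condition 1, and b2 is Condition 3 minus Condition 1. The interaction is the same under both codings, and so is the fit.

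**Step 2: standard errors.** With n per cell and residual SD σ:
- Coded coefficient: σ·√(1/n + 1/n) = σ·√(2/n). At n = 40 this is 0.2236σ.
- Marginal effect: σ·√(4 × 0.25/n) = σ·√(1/n). At n = 40 this is 0.1581σ.
- Ratio: √2 = 1.414, whatever σ, n or r. At n = 42 the two are 0.2182σ and 0.1543σ, with the same ratio. In the moderately unequal allocations tried, it ran from about 1.36 to 1.45.

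**Step 3: power per factor.** Noncentral t with noncentrality d/SE, σ = √(1 - r²), and error df 156 without the covariate or 155 with it. Each entry is coded coefficient vs marginal effect, 40 per cell:

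| d | r = 0 | r = 0.5 | r = 0.7 |
|---|---|---|---|
| 0.4 | 43% vs 71% | 54% vs 83% | 70% vs 94% |
| 0.5 | 60% vs 88% | 73% vs 95% | 88% vs 99% |
| 0.6 | 76% vs 97% | 87% vs 99% | 96% vs >99% |

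With 42 per cell and r = 0: 63% vs 90% at d = 0.5, and 78% vs 97% at d = 0.6. Regression simulations with both effects at 0.6 SD agreed at 40 per cell: 77% vs 97% at r = 0, and a standard-error ratio of 1.414 at every r.

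**Step 4: when effects are not additive.** The two definitions then estimate different things, and either can have the higher power.
- Only Condition 4 lower, by 0.5 SD: both coded coefficients are 0, while both marginal effects are -0.25 SD.
- Only Condition 1 works, at 0.6 SD (r = 0, 40 per cell): each simple effect is 0.6 SD with 76% power; each marginal effect is 0.6/2 = 0.3 SD with 47% power.

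**Step 5: Stage 3 choice, illustration only.** Suppose an effect means p < 0.05 in the favourable direction (the plan sets no threshold), with r = 0 and 40 per cell. Both factors are found in 45% of runs with simple effects vs 78% with marginal effects if the effects are additive at 0.5 SD. If only Condition 1 works at 0.6 SD, the figures are 64% vs 22%.

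**The case against.** The strongest reply is that the plan lists predictors and never says that the mechanism test is the t-test on each coded coefficient. The marginal effects can be had from the same fit, and a careful analyst would request them. The sentence about also exploring the interaction can be read as an additive model first and the product term second; 0/1 coding without the product term already gives the smaller standard error. Marginal versus simple is also partly a choice of question: the plan makes its favoured condition the reference cell, and if only that condition works the simple effects have more power.

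Part of this stands. The loss is conditional on reading the coefficients as labelled, and it is one of precision, not validity, under additivity. The Stage 3 consequence is limited: the choice is among Conditions 1 to 3, which the simple effects compare directly, and it also rests on qualitative profiles and joint judgement.

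It does not remove the point. The sentence that defines the predictors includes the interaction, no additive-first model or marginal contrast is described, and the main-effects label invites the misreading. The plan's own expected pattern is additive, which is where the coded coefficients do worse.

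**Conclusion.** The concern holds, at minor severity. That the coded coefficients are Condition 2 minus 1 and Condition 3 minus 1 is algebra and needs no assumption. The factor of 1.41 is exact for equal cells, which the plan does not state.

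The power cost rests on the assumed alpha, effect sizes and baseline correlation. Over the range shown with 40 per cell, the gap per factor runs from 28 percentage points (43% vs 71%) down to about 4 (96% vs more than 99%), narrowing as the effect or the correlation grows. These figures apply to additive effects; without additivity the ordering can reverse.

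What an effect means in the Stage 3 choice is a separate matter of missing detail. Neither definition is better throughout, and simple effects are a legitimate reading there.

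**What to change.** For the Aim 2 mechanism test:
- Code both factors -0.5/+0.5, or specify marginal contrasts of the four cell means. Keep the product term and baseline intentions.
- Report the interaction and, by name, the simple effects Condition 1 vs 2 and Condition 1 vs 3, so that a non-additive pattern is visible.
- Test the same marginal main effects, on change in intentions, if the repeated measures ANOVA is used.

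For the Stage 3 choice, it would help to state in advance which contrast counts as an effect. The marginal definition need not be imposed there.

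The cost is two or three sentences of analysis-plan wording. No new data are needed, and the fitted model and its R-squared are unchanged, so all contrasts come from one fit.

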### Parents enrolled in Aim 3 will be:

- a) Asked to use a tablet-based application that provides either self-persuasion intervention developed in Aim 2 or HPV Vaccine information only,
- b) Audiorecorded having a discussion with their child's provider, and
- c) Asked questions about their experiences using the tablet and their communication with the provider.

Patients will be identified through EMR review, by ICD-9 or procedure codes, through HIPAA-compliant methods, which will enable our team to invite patient parents with the permission of the Parkland Medical Director ([name]). Parents of patients will be mailed an invitation letter on Parkland letterhead and signed by Drs. [name] and [name] requesting participation in a "study to improve patient satisfaction with healthcare and delivery of vaccines/shots." The letter will provide a telephone number parents can use to ask questions or notify staff of refusal. Letters will be sent in English or Spanish based on the family's preferred language listed in the EMR.

Following the mailing, parents of patients who have not refused contact will be called by a bilingual research assistant (RA). The RA will explain the project and screen parents for eligibility. The RA will screen parents by asking: 1) if their child has ever had the vaccine (yes/no), 2) whether they had ever heard of the vaccine (yes/no), and 3) what best describes their thoughts about it (never thought, undecided, do not want, or do want). Parents who are undecided or never thought about the vaccine will be invited. If the parent agrees, the RA will obtain

verbal consent, administer the baseline survey, and arrange to meet the parent at either UT Southwestern Medical Center (Aim 1a), a Parkland clinic at a chosen time (Aim 1a and Aim 2), or at a Parkland clinic prior to an upcoming appointment (Aims 1b and 3).. Up to 6 contact attempts (3 day, 3 night) will be made. Based on data from previous projects, we expect 6-8% will actively refuse, 13-15% will have a non-working number, and 20-22% will be unreachable. For Aim 3, parents will be sent a letter, and eligibility will be determined in-person before the child's upcoming medical appointment. Eligibility criteria for Aim 3 will be determined by asking the parent if their child has ever had the HPV vaccine (yes/no). If never had the vaccine, the parent will be invited in clinic that day and consent will be obtained.

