During the study appointment, a bilingual RA will 1) obtain HIPAA authorization to review the adolescent patient's EMR, and 2) instruct the participant on how to use either the English or Spanish version of the tablet application. For Aims 1a and 2, the study appointment will last about 60 minutes and will be audio-recorded. For Aims 1b and 3, pre-clinic visit study activities will take 10-20 minutes; post-visit activities will take another 20-25 minutes. All study staff will be trained by Drs. [name] and [name]. Parent participants will receive a \$50 honorarium in the form of a gift card.

We will conduct study visits with a total of 369 parent participants. We expect very few parents will be fathers (<5%; n = 19) and have powered our analysis to only analyze data from mothers of adolescent patients (n = 350). For Aim 1, we will enroll 106 parents: 53 for formative research on self-generated arguments (Aim 1a), and 53 to characterize parent-provider discussions about the HPV vaccine (Aim 1b). For Aim 2, 168 parents will be enrolled for self-persuasion intervention conditions comparing levels of choice and cognitive processing. We will enroll 95 parents for Aim 3, recording provider/patient interaction and testing of tablet-based application. We expect to enroll 18 providers in order to audiorecord the parent-provider discussions for Aims 1b and 3.

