**Stage 2:** To accomplish Aim 2, we will randomly assign 168 undecided parents (of 84 girls & 84 boys) to 1 of 4 intervention conditions that differ by levels of cognitive processing and choice. In a 1-hour study session, parents will use a tablet-based application that directs them to either: verbalize their own arguments based on topics they choose (deep processing, high choice), verbalize arguments based on topics assigned to them (deep processing, low choice), listen to arguments based on topics they choose (shallow processing, high choice), or listen to arguments based on topics assigned to them (shallow processing, low choice). We will conduct exit interviews to assess parents' perspective on the tablet application, self-persuasion condition, and how their beliefs and experiences shape feelings about the HPV vaccine. Adolescents who accompany their parent to the study appointment at their Parkland clinic will have the opportunity to receive the 1st HPV vaccine dose from a Parkland nurse immediately after the exit interview. We will synthesize quantitative and qualitative data to select the optimal intervention condition for that will be used in Stage 3.

**Stage 3:** To accomplish Aim 3, we will recruit from pediatric neighborhood and school-based clinics, with a target of 15 parents per site (n=95). Parents will be randomly assigned to either: 1) self-persuasion plus information (optimal intervention condition from Aim 2; n=48), or 2) HPV information only (n=47). For the self-persuasion group, we will follow procedures in Stage 1. Parents in the information only group will be given a tablet and instructed to listen to information about HPV infections and the benefits and risks of the HPV vaccine. We will audiorecord the parent-provider discussion. Immediately after the visit, an RA will conduct an exit interview in which participants will be asked questions about their experiences using the tablet and their communication with the provider.

We expect to review the medical records of 369 adolescents whose parents were enrolled in our study. Medical records will be reviewed after 12 months for HPV vaccine dates. We will also abstract info for 3 other vaccines (TDAP, MCV4, & influenza) that are correlated with HPV vaccination.

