### Project Timeline

Project Timeline	Year 1				Year 2				Year 3				Year 4				Year 5			
	Q1	Q2	Q3	Q4																
IRB & staff training																				
Advisory Committee meetings																				
Meetings with communication consultant, [name]																				
Build study database & CATI software for surveys																				
Build, pretest, refine, & tech support for the self-persuasion tablet																				
Use EMR to identify eligible patients for each stage																				
Stage 1: Define intervention content (Aim 1)																				
Conduct cognitive interviews of self-generated arguments (n=50)																				
Transcribe recordings and code interview data																				
Clinic launch meeting for recording discussions																				
Recruit & audiorecord parent-provider discussions (n=50)																				
Apply [name]'s coding scheme to transcribed data on discussions																				
Stage 2: Optimize intervention's effects (Aim 2)																				
Refine tablet program for 4 self-persuasion intervention conditions																				
Recruit & conduct proof of concept study (n = 160)																				
Analyze & synthesize quantitative and qualitative data																				
Select self-persuasion intervention condition for Stage 3																				
Stage 3: Assess feasibility in safety-net clinics (Aim 3)																				
Clinic launch meeting for pilot RCT																				
Conduct pilot including audiorecord discussions (n =90)																				
Code parent-provider discussions																				
Analyze data & publish manuscripts																				

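### Aim 2 lets the data choose the primary model: baseline intentions are adjusted for only if two unspecified checks pass, although parents are randomised

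*Combined protocol and SAP*

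**What the plan says.** Under Additional Procedures for Each Stage, Stage 2 is a randomised 2x2 comparison: "we will randomly assign 168 undecided parents" to four conditions formed by choice and cognitive processing. Measurement of Primary Outcomes makes change in vaccine intentions the Aim 2 primary outcome.

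The Analysis Plan for Aim 2 (Biostatistics, Quantitative Analysis) fits a linear regression with 0/1 codes for the two factors and their interaction. On the baseline score it says: "If equivalence assumptions of initial scores and parallel regression slopes for the groups are met, baseline intentions will be included as a covariate". The next sentence is: "If not, repeated measures ANOVA will be used". It names no test, no threshold and no decision-maker for the two conditions. It also does not say which effect in the repeated-measures model would be the primary test.

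The same section plans baseline testing of other variables ("demographic characteristics will be compared at baseline via two-way ANOVA or chi-square tests"). It carries the approach over to the secondary outcome: "We will use a similar analytic strategy to examine the effects of choice and processing on decisional balance". No other part of the document fixes one model whatever the data show.

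**The concern.** Equal starting scores are not a precondition for baseline adjustment in a randomised comparison. Any difference is chance, and adjustment is most useful when a chance difference is large. The plan reverses this: a failed equivalence check moves the analysis to a method that does not correct for the imbalance. With one measurement before and one after (assumed), the group-by-time test in repeated-measures ANOVA is the comparison of change scores, which fixes the pre-to-post slope at 1 instead of estimating it.

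The slopes condition is not needed either. In a balanced randomised design the common-slope regression remains a valid test of the average effect when slopes differ.

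There are two readings. On the natural one, both conditions are checks on the data, in line with the planned baseline tests of demographics. On a lenient one, randomisation satisfies equivalence and only the slopes check can trigger the switch. On both, the data choose the primary model.

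The result matters because, in the Synthesis of Quantitative and Qualitative Analyses, the Stage 3 condition depends on which factor affects intentions, and a condition without an effect on intentions is ruled out. That choice goes into the 95-parent pilot.

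**Working it through.** **Inputs from the document.** 168 parents in four conditions: 168/4 = 42 per cell, 168/2 = 84 v 84 for each main effect (equal allocation assumed; no ratio is stated). The plan says the investigators "have powered our analysis to only analyze data from mothers of adolescent patients", 350 of 369 parents; 168 x 350/369 = 159, and the Project Timeline gives 160, so 40 per cell was also tried.

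**Assumptions.** The document gives no alpha, check level, correlation, SD, slope, effect size or number of time points for Aim 2, so there is no planned figure to reproduce. Assumed: two-sided 5% tests; both checks at 5%; one pre and one post score, normal; pre-post correlation r from 0.3 to 0.8; post/pre SD ratio k from 0.8 to 1.5; effect 0 or 0.4 post SD. The SD range allows for screening that may narrow baseline scores ("Parents who are undecided or never thought about the vaccine will be invited"). The tested effect is averaged over the other factor, with the interaction in the model.

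**Step 1: how often the model switches.** Two roughly independent 5% checks give 1 - 0.95 x 0.95 = 9.75%. Simulation gives about 9.8%, about half of it (4.8% of trials) from slopes alone.

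**Step 2: efficiency of the fallback.** At k = 1, the variance ratio of change score to adjusted estimate is 2(1-r)/(1-r²) = 2/(1+r): 1.54, 1.33 and 1.18 at r = 0.3, 0.5 and 0.7.

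**Step 3: bias after a chance imbalance.** Given a baseline difference D on the tested factor, the change score is biased by (b-1)D, with b = r x k; the adjusted estimate is not. For 84 v 84 the SE of D is sqrt(2/84) = 0.154 SD. Among the 5% of trials where D is significant, its mean size is about 0.36 SD. At r = 0.5, k = 1:

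- bias = -0.5 x 0.36 = -0.18
- critical value of the change-score test = 1.96 x 0.154 = 0.30
- SD of the estimate given D = sqrt(1-0.25) x 0.154 = 0.134
- rejection under no effect ≈ Φ((-0.30 + 0.18)/0.134) ≈ 18%; simulation gives 19%.

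Simulated fallback type I error after a significant imbalance on the tested factor (500,000 trials per setting, 42 per cell; adjusted model about 5% throughout):

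| SD ratio k | r = 0.3 | r = 0.5 | r = 0.7 | r = 0.8 |
|---|---|---|---|---|
| 0.8 | 33% | 29% | 26% | 24% |
| 1.0 | 24% | 19% | 13% | 10% |
| 1.25 | 16% | 11% | 6% | 5% |
| 1.5 | 12% | 7% | 5% | 8% |

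The bias vanishes where r x k = 1, for example 0.8 x 1.25. With 40 per cell, the k = 1 row is 24%, 18%, 13%, 10%. If imbalance is instead flagged by a four-group F-test (separate run, 40,000 trials per setting, k = 1), the figures are about 15%, 11% and 9.5% at r = 0.3, 0.5 and 0.7.

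**Step 4: average over all randomisations, parallel slopes.** Mean bias is about 0. Type I error of the whole rule is 5.0% to 5.7% (four-group baseline check) or 5.0% to 6.3% (check on the tested factor), against 5.0% always adjusted. Power loss at 0.4 SD is at most 2.0 points at k = 1, 2.7 at k = 0.8 and 0.8 at k = 1.5. With the slopes check alone (lenient reading), type I error is 5.0% and power loss 0 to 1.4 points.

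**Step 5: slopes that truly differ.** With slopes 0.4 v 0.6, power falls from 84.3% to about 82%. With 0.3 v 0.7, the rule switches in about 70% of trials and power falls from 84.3% to about 76%. Always-adjusted type I error stays at 5.0% in both.

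**Step 6: the missing threshold.** At r = 0.5, k = 1, moving both checks from the 5% level to 10% or 20% raises switching from about 10% to 19% or 36%, and the power loss from 1.3 to 2.4 or 4.4 points.

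**The case against.** The strongest reply is that almost nothing is lost on average. The rule is written down in advance, both models target the same average effect under randomisation, repeated-measures ANOVA still uses the baseline score, and the primary outcome is itself defined as change. The fallback's bias exists only given a chance imbalance. The larger conditional figures come from a check on the tested factor; a check across all four groups, arguably closer to the plan's wording, gives smaller ones. The larger power losses need unequal slopes that nothing in the document supports. The Stage 3 choice has no p-value threshold, draws on qualitative findings too, and leads only to a feasibility pilot.

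Most of this stands as a limit on size. It does not justify the switch. A rule without a test or threshold is not fully prespecified, and Step 6 shows that its behaviour depends on that gap. Using baseline with the slope fixed at 1 is not the same as adjusting for it, and is the weaker choice when an imbalance has occurred.

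A further point is fair: with 0/1 codes and an interaction, each main-effect coefficient is a simple effect in 42 v 42, not the averaged effect simulated here. For that coefficient, always-adjusted power at 0.4 SD and r = 0.5 is about 56%, not 84%. The comparison keeps its direction (the rule gives about 54%), but the power levels above apply to the averaged contrast.

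**Conclusion.** The concern holds as a minor flaw in prespecification. The Aim 2 primary model depends on the observed data through two conditions that randomisation makes unnecessary. With parallel slopes and checks at 5%, the average cost is at most 1.3 points of type I error and 2.7 points of power. It is larger after a flagged imbalance, depending strongly on correlation and SD ratio and sometimes vanishing, and it is larger if slopes truly differ.

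That the model is conditional follows from the text alone. Every figure for its size rests on the assumed correlations, SD ratios, slopes, check levels, effect size, equal cells and two time points. In the settings compared with parallel or unequal slopes, the rule showed no power advantage over always adjusting on average.

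**What to change.** In the Analysis Plan for Aim 2, make the linear regression with baseline intentions always included the single primary analysis, whatever the observed baseline difference or slopes. Delete the equivalence and slopes conditions and the switch to repeated-measures ANOVA. Examine slope heterogeneity through mean-centred baseline-by-factor terms and, if wanted, report repeated-measures ANOVA; label both as sensitivity analyses that cannot replace the primary model. State whether each main effect is averaged over the other factor. Apply the same rule to decisional balance.

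The core change is two sentences of plan wording. It needs no new data and no more parents, because both models already use baseline intentions.
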